8.3.2 List of Graphs

- Lineplots of body-weight-adjusted IgG-normalized VRC07-523LS levels for each specimen type, by specimen type, assigned sex at birth and treatment arm (“visit week” as x-axis variable. Note, the spacing between two consecutive visit weeks indicate the actual number of weeks between them.) (all treatment arms plotted together but distinguished using different colors).
- Lineplots of body-weight-adjusted protein-normalized VRC07-523LS levels for each specimen type, by specimen type, assigned sex at birth and treatment arm (“visit week” as x-axis variable. Note, the spacing between two consecutive visit weeks indicate the actual number of weeks between them.) (all treatment arms plotted together but distinguished using different colors).
- Lineplots of body-weight-adjusted IgG-normalized VRC07-523LS levels for each specimen type, with sex at birth combined, by treatment arm (“visit week” as x-axis variable. Note, the spacing between two consecutive visit weeks indicate the actual number of weeks between them.) (all specimen types plotted together, separated for treatment arm).
- Lineplots of body-weight-adjusted protein-normalized VRC07-523LS levels for each specimen type, with sex at birth combined, by treatment arm (“visit week” as x-axis variable. Note, the spacing between two consecutive visit weeks indicate the actual number of weeks between them.) (all specimen types plotted together, separated by treatment arm).
- Lineplots of body-weight-adjusted IgG-normalized VRC07-523LS levels for each specimen type, by specimen type, assigned sex at birth and treatment arm (Actual number of days since enrollment as x-axis variable.) (all treatment arms plotted together but distinguished using different colors).

- Scatterplots of correlation as following:
 - Correlation analysis in rectal biopsy, cervical biopsy, vaginal biopsy, rectal secretions, cervicovaginal secretions, and semen, with sex at birth combined and treatment arms combined, by visit, for IgG-normalized and dose-amount-adjusted VRC07-523LS concentration (with Spearman's rank correlation coefficient for raw values and associated p-value category included. The data points included in the visualization will use different symbols reflecting assigned sex at birth, different colors will be used for different treatment arm. The correlation coefficients will base on all data included in the plot).
 - Correlation analysis in rectal biopsy, cervical biopsy, vaginal biopsy, rectal secretions, and cervicovaginal secretions for females with treatment arms combined, by visit, for IgG-normalized and dose-amount-adjusted VRC07-523LS concentration (with Spearman's rank correlation coefficient for raw values and associated p-value category included, different colors will be used for different treatment arm).
 - Correlation analysis in rectal biopsy, semen, and rectal secretions for males, with treatment arms combined, by visit, for IgG-normalized and dose-amount-adjusted VRC07-523LS concentration (with Spearman's rank correlation coefficient for raw values and associated p-value category included, different colors will be used for different treatment arm).
 - Correlation analysis in different specimen types with sex at birth combined, by treatment arm and visit, for IgG-normalized VRC07-523LS concentration (with Spearman's rank correlation coefficient for raw values and associated p-value category included. The data points included in the visualization will different symbols reflecting assigned sex at birth. The correlation coefficients will base on all data included in the plot).
 - Correlation analysis in rectal biopsy, cervical biopsy, vaginal biopsy, rectal secretions, and cervicovaginal secretions for females, by treatment arm and visit, for IgG-normalized VRC07-523LS concentration (with Spearman's rank correlation coefficient for raw values and associated p-value category included, different colors will be used for different treatment arm).
 - Correlation analysis in rectal biopsy, semen, and rectal secretions for males, by treatment arm and visit, for IgG-normalized VRC07-523LS concentration (with Spearman's rank correlation coefficient for raw values and associated p-value category included, different colors will be used for different treatment arm).
 - Correlation analysis of total IgG levels and total protein levels in rectal biopsy, semen, and rectal secretions, by treatment arm, assigned sex at birth, and visit (with Spearman's rank correlation coefficient for raw values and associated p-value category included); treatment groups may also be pooled together to construct correlation matrices.

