Preliminary Results are determined using the ELISA Plate Reader (Molecular Devices) SpectraMax i3X absorbance (Hemoglobin) and fluorescence (protein concentration). Assays are assessed for QC using the standards ran on each plate.

The Quant-iT™ Protein Assay Kit (Invitrogen™) is used to measure the total protein in samples provided by study participants. The kit provides concentrated assay reagent, dilution buffer, and pre-diluted BSA standards. Simply dilute the reagent, load it into the wells of a microplate, add 1-20 µL of sample, mix, then measure the fluorescence. The assay is highly selective for protein and exhibits very little protein-to-protein variation. The assay is performed at room temperature, and the signal is stable for 3 hours. Common contaminants, such as salts, solvents, or DNA—but not detergents—are well tolerated in the assay.

Bio-Plex Pro™ Human Isotyping Assay for IgG concentration

The Bio-Plex Pro™ Human Isotyping Assay (Bio-Rad Laboratories, Inc.) is used to measure IgG in mucosal samples provided by study participants. The kit provides magnetic beads, detection antibodies, standards, controls, and reagents for detecting human IgG1, IgG2, IgG3, IgG4, IgA, and IgM. Samples are diluted in the provided kit buffer and mixed with the multiplex magnetic bead panel in a 96-well plate. Plates are washed with the kit-provided wash buffer, and secondary detection antibodies are added per the package insert instructions. Plates are read on a BioPlex 200 instrument to measure Fluorescence Intensity (FI). Mean Fluorescence Intensity (MFI) values are used to quantify isotype concentrations. Sample isotype concentrations are derived from the kit-supplied standard curve.

Specimens

A total of 24 participants and 504 secretion (semen, cervicovaginal, and rectal) samples (168 of each specimen type) will be tested at 7 timepoints (visits 2, 4, 5, 6, 7, 8 and 9) from Groups 1 and 2. A total of 24 participants and 168 serum samples will be also tested at 7 timepoints (visits 2, 4, 5, 6, 7, 8 and 9) from Groups 1 and 2. A total of 24 participants and 288 biopsy (colorectal, cervical and vaginal) samples (96 of each specimen type) will be tested at 4 timepoints (visits 2, 4, 8 and 9) from Groups 1 and 2.

Summary of sample numbers and specimen types proposed for testing is summarized in the table below:

No. of Participants	Specimen Type		Timepoint (visit)	Total no. of samples
24	Secretion	Semen	2,4,5,6,7,8,9	168
		Cervicovaginal	2,4,5,6,7,8,9	168

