		Rectal	2,4,5,6,7,8,9	168

24	Biopsy	Colorectal	2,4,8,9	96
		Cervical	2,4,8,9	96
		Vaginal	2,4,8,9	96

Statistical endpoints

To account for heterogeneity in size of biopsies and absolute concentration (e.g., rectal secretions flushed with media during collection) of the samples, IgG- and protein-normalizations for mucosal samples are performed by dividing VRC07-523LS levels (pg/mL) by the total IgG (ng/mL) and protein concentrations (mg/mL), respectively, as following:

- VRC07-523-LS concentration normalized by total IgG (pg VRC07-523LS/ng total IgG):
 - Units: VRC07-523LS units are pg/mL, and total antibody units are ng/mL. Truncate as specified in the Truncation Rule section below.
 - Antibody normalized concentration = truncated observed concentration / truncated total antibody
- VRC07-523-LS concentration normalized by total protein (pg VRC07-523LS/ng total protein):
 - Units: VRC07-523LS units are pg/mL, and total protein units are mg/mL (milligrams per milliliter). To convert mg to ng, first truncate as specified in the truncation rule section below, then multiply total protein by 1×10^6 (1,000,000).
 - Protein normalized concentration = truncated observed concentration / (10^6 x truncated total protein)

IgG-normalizations for serum samples are performed by dividing VRC07-523LS levels (μ g/mL) by the average reference values for total IgG concentrations in serum in the USA (1165 mg/dL), as following:

- VRC07-523-LS concentration in serum normalized by total IgG (pg VRC07-523LS/ng total IgG):
 - Units: VRC07-523LS units are μ g/mL, and total antibody units are mg/dL. Truncate as specified in the Truncation Rule section below, then divided total antibody by 100.
 - Antibody normalized concentration = truncated observed concentration / (10^{-2} x U.S. reference total antibody)

Truncation rules are applied for SMCxPro, serum, total IgG, and total protein data as following:

- SMCxPro truncation: For results under the smaller value of limit of detection (LLoD) and sample type specific limit of quantification (LLoQ), they are truncated at lower limit of quantification (LLoX) / 2 where LLoX is minimum(LLoQ, LLoD)
- serum truncation: Baseline serum concentrations below the lower limit of quantification (LLoQ = 45.7 ng/ml = 0.0457μ g/ml) are replaced with LLoQ/2. No post-baseline concentrations are below the LLoQ.

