- Total IgG truncation: Total IgG (total IgG = Hu IgG1 + Hu IgG2 + Hu IgG3 + Hu IgG4). Any missing subclass will be treated as zero for the purpose of calculating total IgG. If IgG1, IgG2, IgG3, and IgG4 subclasses are all missing for a sample, the sample will be treated as not collected/no sample recovered, and total IgG will be set to NA. Total IgG concentration will be compared to 48 ng/mL; if it is less than 48 ng/mL, the sample will be flagged in the analysis dataset and excluded from the analysis without truncation.
- Total protein truncation: Compared total protein concentration to 0.167 mg/mL, which will be the last curve point and considered as the LLoQ. If concentration < 0.167 mg/mL, then it will be truncated as $0.5 * 0.167$ mg/mL

Body-weight adjustment will be performed by dividing the IgG- and protein-normalized VRC07-523LS levels by the body weight at baseline. Dose-amount adjustment will be performed by dividing the IgG- and protein-normalized VRC07-523LS levels by the body weight at baseline multiplied the dose amount of the products (T1: 10 mg/kg VRC07-523LS, T2: 30 mg/kg VRC07-523LS). The % penetration into different mucosal compartments will be calculated as the protein-normalized VRC07-523LS level in each of the mucosal specimen type divided by that in serum, multiplied by 100.

Pre-treatment participants and all secretion samples deemed hemoglobin-contaminated or unreliable (1. Total IgG concentration < 48 ng/mL, or 2. Total protein concentration < 0.167 mg/mL, with total IgG concentration also < 48 ng/mL) are excluded from the analysis.

Statistical methods

Tabular summaries of the distributions of body-weight-adjusted, IgG- and protein-normalized VRC07-523LS levels, and % penetration of protein-normalized VRC07-523LS is presented by specimen type, treatment arm, sex at birth and visit. Body weight comparisons between treatment arms (T1 vs. T2) and between sexes at birth (Female vs. Male) are presented using the Wilcoxon Rank Sum Test. A table of partial Spearman's rank correlation coefficients of specimen comparison and p-values, adjusted for treatment group (T1 vs. T2) and sex at birth (males vs. females), is presented by visit. P-values are adjusted for multiple comparisons by controlling the false discovery rate (FDR) using the Benjamini-Hochberg procedure [9] and the q-value [10]. Results are significant if the adjusted p-value or q-value ≤ 0.05 .

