- For rectal biopsies, dose-amount-adjusted IgG-normalized VRC07-523LS concentrations comparisons at visit 4 among different sexes, using Wilcoxon rank sum test, by specimen type. P-values will be adjusted for multiple comparisons by controlling the false discovery rate (FDR) using the Benjamini-Hochberg (BH) procedure and the q-value. The unadjusted p-values, BH-adjusted p-values, and q-values will be reported.
- Specimen comparison using partial Spearman's rank correlation, adjusted for treatment arms (T1 and T2) and sex assigned at birth, stratified by visit. P-values will be adjusted for multiple comparisons by controlling the false discovery rate (FDR) using the Benjamini-Hochberg (BH) procedure and the q-value. The unadjusted p-values, BH-adjusted p-values, and q-values will be reported.
- Summary of the percentage of penetration for protein-normalized VRC07-523LS concentration, by specimen type, treatment arm, assigned sex at birth and visit.
- For secretions, comparisons between visits 4, 6, and 8 penetration percentages (protein-normalized VRC07-523LS of mucosal divided by serum at Cmax after a different number of infusions) using Wilcoxon signed-rank test, by specimen types with treatment groups combined. P-values will be adjusted for multiple comparisons by controlling the false

discovery rate (FDR) using the Benjamini-Hochberg (BH) procedure and the q-value. The unadjusted p-values, BH-adjusted p-values, and q-values will be reported.

- For secretions, comparisons between visits 2, 5, 7, and 9 penetration percentages (protein-normalized VRC07-523LS of mucosal divided by serum at trough after a different number of infusions after a different number of infusions) using Wilcoxon signed-rank test, by specimen types with treatment groups combined. P-values will be adjusted for multiple comparisons by controlling the false discovery rate (FDR) using the Benjamini-Hochberg (BH) procedure and the q-value. The unadjusted p-values, BH-adjusted p-values, and q-values will be reported.

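### The pooled-arm, dose-adjusted specimen correlations are not restricted to post-infusion visits; at drug-free visit 2 the dose divisor alone can produce a positive correlation

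*SAP*

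**What the plan says.** **Which correlations.** SAP 8.3.2 specifies scatterplots and Spearman coefficients among rectal, cervical and vaginal biopsies, rectal and cervicovaginal secretions, and semen. The first set is "with sex at birth combined and treatment arms combined, by visit, for IgG-normalized and dose-amount-adjusted VRC07-523LS concentration". The next two bullets repeat this for females and for males, again with arms pooled and on the dose-amount-adjusted scale. The Statistical methods text of 8.3 describes the same plots. None of these places lists visits. SAP 8.3.1 adds a table: "Specimen comparison using partial Spearman's rank correlation, adjusted for treatment arms (T1 and T2) and sex assigned at birth, stratified by visit". It names neither the visits nor the measurement scale.

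**Which visits exist.** SAP 8.3 (Specimens) says of secretions that "samples (168 of each specimen type) will be tested at 7 timepoints (visits 2, 4, 5, 6, 7, 8 and 9"; biopsies are tested at visits 2, 4, 8 and 9. Visit 2 is the D-14 baseline collection, and Protocol 9.3 places randomization after that collection.

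**How a value is built.** For low mucosal results, "they are truncated at lower limit of quantification (LLoX) / 2 where LLoX is minimum(LLoQ, LLoD". Then "Antibody normalized concentration = truncated observed concentration / truncated total antibody". The dose-amount adjustment divides these "levels by the body weight at baseline multiplied the dose amount of the products (T1: 10 mg/kg VRC07-523LS, T2: 30 mg/kg VRC07-523LS".

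**What is excluded.** The end of the Statistical endpoints text in SAP 8.3 removes pre-treatment participants and contaminated or unreliable secretion samples from the analysis. The next paragraphs and SAP 8.3.1 nevertheless plan dose-normalized comparisons of visit 2 with visits 5, 7 and 9 in secretions and with visit 9 in tissue.

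**The concern.** At visit 2 the dose has been neither given nor assigned. The factor 10 or 30 then measures nothing about the sample, but it enters both axes of every pooled-arm plot. If the antibody signal is only background or a fill-in, the two arms separate in the same direction in both specimens, and a rank correlation across pooled arms picks up that separation.

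Protocol 4.3 intends the baseline biopsies and secretions as negative controls. A negative control that can show a significant antibody correlation makes the genuine post-infusion correlations harder to read. Visit 2 tests would also join the FDR-adjusted family of the partial Spearman table while carrying no information on drug.

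**Working it through.** **1. The plan's own figure.** The documents give no figure for a visit 2 correlation. The nearest is the correlation power in Protocol Table 6-3. With Z' = arctanh(r) + r/(2(n-1)) at r = 0.5, n = 24: Z' = 0.5493 + 0.5/46 = 0.5602. The critical r is 0.4044 (t = 2.074 on 22 df), with arctanh 0.4289. Power = Phi((0.5602 - 0.4289) x sqrt(21)) = Phi(0.602) = 72.6%, as stated. The table is sound; it assumes that a correlation reflects drug.

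**2. The plotted value at visit 2.** If the result is below LLoX:

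value = (LLoX/2) / (total IgG x baseline weight x dose)

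At 75 kg the divisor is 750 x IgG in T1 and 2250 x IgG in T2, a ratio of 3 at equal IgG and weight. A background reading above LLoX that does not depend on arm is shifted by the same factor.

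**3. Expected correlation with no drug.** On the log scale, two specimens from one person share log dose and log weight; total IgG is taken as independent between them.

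- Dose variance with equal arms: (ln 3 / 2)^2 = 0.5493^2 = 0.302
- Weight variance (assumed log-SD 0.18): 0.032
- Shared variance: 0.334, of which dose is 0.302/0.334 = 90%
- Correlation = 0.334 / (0.334 + s^2), where s is the log-SD of total IgG

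| s | 0.3 | 0.5 | 0.8 | 1.0 | 1.5 |
|---|---|---|---|---|---|
| Expected log-scale correlation | 0.79 | 0.57 | 0.34 | 0.25 | 0.13 |

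**4. How many plots, and at what n.** Females supply five specimen types (10 pairs) and males three (3 pairs). One pair, rectal biopsy with rectal secretion, is common to both, so there are 10 + 3 - 1 = 12 distinct pairs at each of visits 2, 4, 8 and 9. At visits 5, 6 and 7 only secretions exist: 2 pairs each. Total 4 x 12 + 3 x 2 = 54, of which 12 fall at visit 2. Eleven of those 12 are single-sex (9 female, 2 male), so n is about 12. Only rectal biopsy with rectal secretion can reach n = 24.

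**5. Chance of p<0.05 with no drug.** Simulated Spearman tests with all values below LLoX, IgG lognormal and independent between specimens, weight log-SD 0.18 and equal arms. Repeat runs moved these by a couple of points.

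| IgG log-SD | 0.3 | 0.5 | 0.8 | 1.0 | 1.5 |
|---|---|---|---|---|---|
| n = 12 (11 pairs) | 97% | 60% | 22% | 12% | 6% |
| n = 24 (1 pair) | 100% | 92% | 41% | 23% | 10% |

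Without the weight x dose division the rate is about 5% at either n.

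**6. Outputs adjusted for arm or run within arm.** The within-arm plots in 8.3.2 are not dose-divided, so they carry no dose artifact. A visit 2 coefficient there, if built on fill-ins, only correlates 1/IgG between specimens. The partial Spearman table adjusts for arm. If it is run on the dose-amount scale, the shared weight remains: with weight log-SD 0.2 and n = 24, p<0.05 occurred in 36, 9, 5 and 6% of runs at IgG log-SD 0.25, 0.5, 0.75 and 1.0.

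**The case against.** **Visit 2 may not be meant to enter.** The bullets list no visits, and the exclusion sentence may be intended to remove pre-treatment data. SAP section 4 limits the randomized cohort to people who received product, so reading the sentence as being about participants leaves it little to exclude. A reader might infer that the SAP states that visit 2 is in the correlations; it does not. What stands is that the exclusion sentence conflicts with the visit 2 comparisons in 8.3 and 8.3.1. Other bullets in 8.3.1 name their visits when they want fewer, and the correlation bullets name none.

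**The size depends on an unknown.** The documents do not give the spread of total IgG. SAP 8.3 justifies normalization by variable biopsy size and flushed rectal secretions, which points towards a wide spread, where the effect is small. This stands, and is why a range is shown.

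**Threefold is not exact.** A reader might infer that every T1 value is three times every T2 value. That holds only at equal IgG and weight. With weight log-SD 0.2, a random T1 value exceeds a random T2 value with probability 0.99, 0.93 and 0.78 at IgG log-SD 0.25, 0.5 and 1.0.

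**Limited consequence.** Coefficients are computed visit by visit, so post-infusion results are untouched. Arms are coloured in the pooled plots, so a split could be seen. The specimens named in these plots do not include serum. A reader might infer that the primary serum-mucosa correlation is compromised; the documents do not support that.

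**Conclusion.** The concern holds as a gap in specification that can yield a false result. As written, the pooled-arm, dose-amount-adjusted correlations run at every assayed visit, and at visit 2 the divisor creates an expected positive coefficient with no drug present. For the typical pair (n about 12) the chance of nominal significance ranges from 97% at IgG log-SD 0.3 to 6% at 1.5. This rests on all values lying below LLoX, independent IgG between specimens and the assumed weight spread.

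The point is confined to visit 2. The arm-adjusted table and the within-arm plots are free of the dose artifact, but their visit 2 entries still say nothing about drug, and the table's visit 2 tests would enlarge its FDR family. The plots support the serum-mucosa primary objective but are not that analysis. The change should be made because it is nearly free, not because the trial's main conclusions are at risk.

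**What to change.** 1. In SAP 8.3.2, and in the partial Spearman bullet of 8.3.1, state that VRC07-523LS correlations are computed at post-infusion visits only: visits 4 to 9 for secretions, and visits 4, 8 and 9 for tissue. Visit 2 tests then stay out of the FDR family.
2. Report visit 2 as the number of samples above LLoX for each specimen type. This keeps its role as a negative control.
3. Reword the exclusion sentence in SAP 8.3 so that it agrees with the planned visit 2 comparisons.

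A blanket ban on dose-dividing visit 2 values is not needed. The paired comparisons of visit 2 with visits 5, 7 and 9 use the same baseline weight and dose for both members of a pair, so the direction of each within-person change is unaffected. Dividing only one member would break them.

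The cost is SAP wording and the removal of the visit 2 correlation output. No drug information is lost.
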